9.4 Database management and quality control

Novartis personnel or a designated CRO will review the data entered by staff at the Investigator's site for completeness and accuracy. Electronic data queries stating the nature of the problem and requesting clarification will be created for discrepancies and missing values and sent to the Investigator's site via the EDC system. Designated Investigator site staff are required to respond promptly to queries and to make any necessary changes to the data.

Concomitant treatments entered into the database will be coded using the WHO Drug Reference List, which employs the Anatomical Therapeutic Chemical classification system. Medical history/current medical conditions and adverse events will be coded using the Medical dictionary for regulatory activities (MedDRA) terminology.

data of spleen imaging readings will be processed centrally and the results for patients enrolled into treatment will be sent electronically to Novartis or a designated CRO.

The occurrence of any protocol deviations will be monitored throughout the study. After these actions have been completed and the database has been declared to be complete and accurate, it will be locked and made available for data analysis. Any changes to the database after that time can only be made by joint written agreement between the Novartis Global Head of BDM and the Global Therapeutic Area Head.

10 Statistical methods and data analysis

The cutoff date of data for the clinical study report (CSR) will be when all the patients either complete the Week 24 Visit or discontinue the study, whichever comes first. The primary analysis will be performed at that date of data cutoff. An interim analysis is planned to be performed when the first 50 patients either complete the Week 24 Visit or discontinue the study. Additionally, follow-up efficacy and safety data will also be summarized in a separate report.

10.1 Analysis sets

10.1.1 Full Analysis Set

The Full Analysis Set (FAS) comprises all patients who received at least one dose of INC424.

10.1.2 Safety population

The Safety population (SAF) consists of all patients who received at least one dose of INC424 and had at least one safety evaluation post-Baseline. This analysis set will be used for all safety analyses.

10.1.3 Per-Protocol Set

The Per-Protocol Set (PPS) consists of all patients in the FAS who did not meet the criteria for major protocol deviations.

10.2 Patient demographics/other Baseline characteristics

Demographic and other Baseline data (including disease characteristics) will be summarized descriptively for the FAS. Qualitative data such as sex and gender will be summarized by means of the contingency table. Quantitative data such as age and body weight will be summarized descriptively including the mean, standard deviation, median, minimum and maximum.

Medical history will be tabulated with the number and percentage of patients with medical history for each system/organ class.

All demographic and other Baseline data will also be listed.

10.3 Treatments (study treatment, concomitant therapies, compliance)

The duration of exposure in days to INC424 will be defined as the time between the date of last dosing and the date of first dosing. It includes periods of temporary interruptions of INC424. The duration of exposure will be calculated for each patient, and will be summarized descriptively.

The average daily dose (mg/day) will also be calculated on a per patient basis. It is defined as the ratio of the cumulative dose to the duration of exposure. The average daily dose will be summarized descriptively.

The number and percentage of patients with dose change/dose interruption (dose change to zero mg) will be calculated by the reason for dose change.

Concomitant medications will be listed in detail and tabulated by WHO drug class.

10.4 Primary objective

The primary objective is to determine the efficacy of INC424 as assessed by reduction in spleen volume.

10.4.1 Variable

The primary efficacy variable is the proportion of patients achieving \geq 35% reduction in spleen volume from Baseline to Week 24 as measured by MRI (or CT scan).

10.4.2 Statistical hypothesis, model, and method of analysis

The primary analysis will be based on a single-sample binomial test (normal approximation) at the one-sided 2.5% significance level, analyzed in the FAS. Note that a patient with a missing spleen volume at Baseline will be excluded from the denominator in the primary efficacy analysis. A patient with a missing spleen volume at Week 24 will be considered as having not achieved the \geq 35% reduction. Patients who drop out of the study due to any reason prior to Week 24 Visit will be considered as having not achieved the \geq 35% reduction.

The statistical hypotheses are

 $H_0: p \le 0.2$ versus $H_1: p > 0.35$,

where p is the proportion of patients achieving $\geq 35\%$ reduction in spleen volume from Baseline to Week 24 as measured by MRI (or CT scan). The null hypothesis will be tested with one one-sided single-sample binomial test (normal approximation) using an overall type I error rate of 2.5%.

The study has a group sequential design and includes a single interim analysis when the first 50 patients either complete the Week 24 Visit or discontinue the study. The boundaries for the single-sample binomial test will be determined using an alpha-spending function (Lan and DeMets 1983) which approximates the boundaries of (O'Brien and Fleming 1979). For example, if exactly 50 patients are included in the interim analysis, then the p-value from the

single-sample binomial test must be ≤ 0.001 to be considered statistically significant. Note that the study will subsequently continue to the final analysis regardless of the statistical significance reached at the interim analysis. When 110patients are exactly included in the final analysis, then the p-value must be ≤ 0.024 to be considered statistically significant. The statistical analysis will be performed using the actual numbers observed at the cut-off date for the interim and the final analyses, the corresponding boundaries will be derived from the prespecified alpha-spending function.

10.4.3 Handling of missing values/censoring/discontinuations

Missing record for spleen volume will not be imputed.

10.4.4 Supportive analyses

An analysis on the PPS will be repeated for the primary efficacy variable.

The primary efficacy variable will be summarized within each of the following subgroups:

- Sex: male or female.
- Country: Japan, Korea, Taiwan or China.
- Baseline prognostic category: Intermediate-2 or High.
- Previous use of hydroxyurea: use or non-use.
- Starting dose: 15 mg BID or 20 mg BID.

Other subgroups may also be considered.

10.5 Secondary objectives

The secondary objectives are to determine the safety of INC424 and to evaluate changes in patient reported outcomes as assessed by the EORTC QLQ-C30 score and Seven-day modified MFSAF v2.0, and to evaluate the duration of response as assessed by reduction in spleen volume.

10.5.1 Change in EORTC QLQ-C30 score from Baseline to Week 24

Data from the EORTC QLQ-C30 questionnaire will be analyzed using the standardized scores. The change from Baseline will be calculated with the data collected at the Baseline Visit as the Baseline. The 5 functional scales, 3 symptom scales, 1 global health status/QOL scales, and 6 single-item scales will be summarized with descriptive statistics by scheduled visit.

10.5.2 Change in total symptom score from Baseline to Week 24 as measured by Seven-day modified MFSAF v2.0

The change in total symptom score from Baseline will be tabulated with descriptive statistics by scheduled visit. All individual scores will also be tabulated with descriptive statistics by scheduled visit.

The percentage of patients who have \geq 50% reduction in total symptom score at Week 24 will be estimated with 95% confidence interval.

10.5.3 Best response rate

The best response rate is defined as the proportion of patients achieving \geq 35% reduction in spleen volume from Baseline at any post-baseline assessment. The best response rate will be estimated with 95% confidence interval.

10.5.4 Duration of maintenance of a greater or equal 35% reduction from Baseline in spleen volume

For patients who had at least one $\geq 35\%$ reduction in spleen volume from Baseline at postbaseline, the duration of response will be calculated. The start date of the duration is defined as the first spleen volume measurement that is $\geq 35\%$ reduction from Baseline, and the end date is defined as the earliest of the following:

- Death
- Any protocol-defined event of disease progression (see Section 6.2.4.1)

Censoring date is defined as the date of the last adequate assessment of the spleen volume. Patients who had more than 1 consecutive missing spleen volume assessment will be censored at the last adequate assessment prior to the consecutive missing assessments, regardless of the occurrence of a subsequent death or any event of disease progression.

The duration of response will be evaluated using a Kaplan-Meier estimate. Note that the analysis will be performed only for patients who achieved a \geq 35% reduction in spleen volume.

10.5.5 Safety

10.5.5.1 Analysis set and grouping for the analyses

For all safety analyses, the SAF will be used. All listings and tables will be presented by Subject ID.

The overall observation period will be divided into two mutually exclusive segments:

- Pre-treatment period: from day of patient's informed consent to the day before first dose of INC424
- On-treatment period: from day of first dose of study drug to 30 days after last dose of INC424

10.5.5.2 Adverse events

Summary tables for adverse events have to include only adverse events that started or worsened during the on-treatment period, the treatment-emergent adverse events. However, all safety data (including those from the pre and post-treatment periods) will be listed and those collected during the pre-treatment are to be flagged.

The incidence of treatment-emergent adverse events (new or worsening from Baseline) will be summarized by system organ class and or preferred term, severity (based on CTCAE grades), type of adverse event, relation to study treatment. Deaths reportable as SAEs and non-fatal serious adverse events will be listed by patient and tabulated by type of adverse event.

Novartis	Confidential	Page 65
Oncology Clinical Trial Protocol		Protocol No. CINC424A2202

Specific safety event categories (SEC) may be considered. Such categories consist of one or more well-defined safety events which are similar in nature and for which there is a specific clinical interest in connection with INC424. Specific SECs are to be defined by the Clinical Team with regular updates as necessary and described in the Report and Analysis plan (RAP). For each specified SEC, number and percentage of patients with at least one event part of the SEC will be reported.

10.5.5.4 Other safety data

12-lead ECGs

12-lead ECGs including PR, QRS, QT, QTcF, QTcB, and RR intervals will be obtained for each patient during the study in accordance with the Schedule of Observations, and will be summarized descriptively. For the calculation of changes and percent changes in cardiac intervals, the average of intervals from the Screening and Baseline recordings will be used as the Baseline for comparison of all post-Baseline intervals.

The proportion of patients with the following outliers in QT, QTcF, or QTcB intervals will be calculated and tabulated by scheduled visit:

- A measured value of >450 ms
- A measured value of >480 ms
- A measured value of >500 ms
- A change from Baseline of >30 ms

• A change from Baseline of >60 ms

Other ECG parameters will also be analyzed as appropriate.

Vital signs

Vital signs including systolic blood pressure, diastolic blood pressure, respiratory rate, body temperature, and pulse will be taken in the seated position for each patient during the study.

The proportion of patients with vital signs out of the following normal ranges will be calculated:

Table 10-1	Criteria for Clinically Notable Vital Sign Abnormalities
------------	--

Parameter	High Threshold	Low Threshold
Systolic Blood Pressure	>160 mm Hg	<85 mm Hg
Diastolic Blood Pressure	>95 mm Hg	<50 mm Hg
Respiratory rate	> 24 per minute	< 8 per minute
Temperature	≥37.5°C	≤35.0°C
Sitting pulse	≥120 bpm	≤50 bpm

The change in weight (kg) and BMI (kg/m²) from Baseline will be summarized descriptively by scheduled visit.

A shift table comparing Baseline with worst on-treatment result will be generated. Also, all vital signs will be listed by patient.

10.5.5.5 Tolerability

The number and percentage of patients who have a dose modification due to a treatmentrelated adverse event will be summarized by type of dose modification (omission, dose reduction, and permanent discontinuation) and preferred term. A listing of all patients receiving INC424 who have a dosing change will include the new dose, interruption, or stopping as well as day since first dose.

10.7 Interim analysis

A single interim analysis is planned to be performed when the first 50 patients either complete the Week 24 Visit or discontinue the study (information fraction is 45.5% for 110 patients, the required sample size for this study). The interim analysis will be performed to show the outstanding efficacy at the interim time-point: there is no futility look. However, note that this trial will not be stopped even if outstanding efficacy was seen at the interim time-point. The primary aim of the interim analysis is to assess the efficacy and safety of INC424 in Asian MF patients earlier and to achieve an earlier regulatory filing to health authorities with the interim efficacy and safety data. If this interim analysis shows at least the pre-specified number of responders, the Steering Committee (SC) will discuss the safety and efficacy results, and will make a final decision on the applicability of a submission.

Test boundaries will be determined using the alpha spending function described by (Lan and DeMets 1983) which approximates the boundaries of (O'Brien and Fleming 1979).

The planned study design was confirmed to fulfill the above conditions via simulations in EAST version 5.3, and the corresponding simulated probabilities and further simulation results are given in Table 10-2.

	First interim	Final analysis
Planned sample size	50	110
Information fraction (%)	45.5	100.0
Cumulative power	0.345	0.951
Stopping boundary (to reject null hypothesis)		
Z-value	3.126	1.965
Number of required responders	19	31

Table 10-2 Design properties of the proposed two stage group sequential design

If the exact number of patients analyzed at the interim and final analyses deviates from 50 and 110 respectively, the actual critical boundaries will be recalculated using the alpha-spending function defined above. In particular, the critical boundary to be used at the interim analysis will be derived from the pre-specified error spending function using the actual number of patients analyzed and assuming 110 patients in the final analysis. Further, the critical value for the final analysis will be calculated using the exact number of patients analyzed at the date of data cutoff, and considering the alpha-level spent at the interim analysis, in order to achieve a cumulative type I error smaller than or equal to 2.5%.

The interim data will be analyzed by statistician in Novartis Japan BDM (Biometrics and Data Management; not independent statistician) because of open-label study and the results will be reviewed by the Steering Committee and pre-determined associates in Novartis who can have an access to the interim results. Therefore, no DMC will be established.

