4.2 Timing of interim analyses

A single interim analysis is planned when the first 50 patients have completed Week 24 Visit or have discontinued from the study prior to Week 24. The primary aim of the interim analysis is to assess the efficacy and safety of INC424 in Asian MF patients and to achieve an earlier regulatory filing to health authorities with the interim efficacy and safety data. If this interim analysis shows at least the pre-specified number of responders (see Section 10.7), the Steering Committee (SC) will discuss the safety and efficacy results, and will make a final decision on the applicability of a submission. Irrespective of this decision, the study will move to the second stage in order to enroll additional patients so that the primary analysis will be performed with approximately 110 patients in total. The alpha for the final analysis will be adapted to alpha spent at the interim analysis (see Section 10.7).

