CSR	Clinical Study Report
СТ	Computer Tomography
CTC	Common Toxicity Criteria
CTCAE	Common Terminology Criteria for Adverse Events
DBL	Database Lock
DI	Dose Intensity
ECG	Electrocardiogram
eCRF	Electronic Case Report Form
EORTC	European Organization for Research and Treatment of Cancer
FAS	Full Analysis Set
IWG-MRT	International Working Group for Myelofibrosis Research and Treatment
MedDRA	Medical Dictionary for Regulatory Affairs
MF	Myelofibrosis
MFSAF	Myelofibrosis Symptom Assessment Form
MRI	Magnetic Resonance Imaging
ms	Millisecond
PD	Protocol Deviation
PD	Pharmacodynamics
PET-MF	Post Essential Thrombocytemia-Myelofibrosis
PK	Pharmacokinetic
PMF	Primary Myelofibrosis
PPS	Per-Protocol Set
PPV-MF	Post Polycythemia Vera-Myelofibrosis
PT	Preferred Term
QoL	Quality of Life
RBC	Red Blood Cell
SAE	Serious Adverse Event
SAF	Safety Analysis Set
SI	Standard International
SMQ	Standard MedDRA Query
SOC	System Organ Class
WBC	White Blood Cell

1 Introduction

This statistical analysis plan (SAP) describes all planned analyses for the final Clinical Study Report (CSR) of study CINC424A2202, a phase II, open-label, multi-center study of the JAK inhibitor INC424.

A single interim analysis was conducted when the first 50 patients had completed the Week 24 visit or discontinued from the study prior to the Week 24 visit. The aim of the interim analysis was to assess the efficacy and safety of INC424 in Asian MF patients and to achieve an earlier regulatory filing to health authorities with the interim efficacy and safety data. The efficacy, safety **analysis** have been performed for 120 patients since the interim analysis showed the positive result. The analysis plan of CSR for Week 24 was documented in "CINC424A2202 RAP Module 3 Detailed statistical methodology Amendment 2" and the results were presented in "the Week 24 CSR" released on Sep 4 2013.

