2.5 Analysis of the primary objective

Primary analysis was conducted and the result was reported in "the Week 24 CSR" and not applicable in this document.

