2.14 Interim analysis

A single interim analysis was conducted by the Novartis statistician.

With regard to detailed plan for the interim analysis, please refer to Section 4.9 in "CINC424A2202 RAP Module 3 Detailed statistical methodology Amendment 2".

3 Sample size calculation

The planned sample size of 110 was determined based on the single-sample binomial test (normal approximation).

Study INCB 18424-351 is a randomized, double-blind, placebo-controlled study comparing the efficacy and safety of INC424 to a matched placebo in patients with PMF or post-PV/ET MF. In this study, the same primary efficacy variable, i.e., proportion of patients achieving \geq 35% reduction in spleen volume from Baseline at Week 24 as measured by MRI (or CT scan), is evaluated. The result of Study INCB 18424-351 provided a response rate of 41.9% in INC424 group while a response rate of 0.7% was observed in the placebo group.

Based on the results obtained in Study INCB 18424-351, the proportion of patients on this study achieving \geq 35% reduction in spleen volume from Baseline at Week 24 as measured by MRI (or CT scan) is expected to be 0.35. From the aspect of clinical benefit in patients with PMF or post-PV/ET MF, a threshold of 0.2 was set for the null hypothesis.

An interim analysis is planned in this study. If the study had no interim analysis (1-stage approach), the required sample size of 110 provides power of 0.951 with one-sided type I error rate of 0.025 under response rate of 0.2 and 0.35 for null and alternative hypotheses. The power for the group sequential (i.e., 2-stage) design accruing 110 total patients with the same final time-point boundary ($\geq 31/110$) and an interim analysis conducted after 50 patients using an O'Brien-Fleming type interim analysis boundary ($\geq 19/50$) is approximately 0.95. Therefore, the effect of the interim analysis on the overall study power is negligible.

4 Change to protocol specified analyses

Not applicable.

5 Appendix

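### The normal-approximation boundaries do not hold the stated 2.5% type I error: 19/50 then 31/110 has an exact error of 2.57%, and the recalculation rule exceeds 2.5% at 9 of the 10 final sizes from 111 to 120

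*Protocol*

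**What the plan says.** Protocol 10.4.2 tests the null response rate of 0.2 with a one-sided "single-sample binomial test (normal approximation) using an overall type I error rate of 2.5" percent. Alpha is split between one interim look at 50 patients and a final look at 110 by a Lan-DeMets spending function of O'Brien-Fleming type. Table 10-2 gives Z boundaries of 3.126 and 1.965, or 19 responders of 50 and 31 of 110. SAP section 3 repeats these counts.

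If the numbers differ from 50 and 110, Protocol 10.7 recalculates the boundaries. The final one takes account of the alpha already spent, "in order to achieve a cumulative type I error smaller than or equal to 2.5" percent. Protocol 4.2 says the same more briefly: "The alpha for the final analysis will be adapted to alpha spent at the interim analysis".

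Protocol 10.4.2 also says that "a patient with a missing spleen volume at Baseline will be excluded from the denominator in the primary efficacy analysis", so the analysed N can be smaller than the number treated.

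The SAP introduction reports that "A single interim analysis was conducted when the first 50 patients had completed the Week 24 visit" or had discontinued, and that analyses "have been performed for 120 patients since the interim analysis showed the positive result". SAP 2.5 records that the primary analysis has been done: "Primary analysis was conducted and the result was reported in" the Week 24 CSR. For the interim, SAP 2.14 points elsewhere: "With regard to detailed plan for the interim analysis, please refer to Section 4.9 in" RAP Module 3 Amendment 2, which is not among the documents.

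**The concern.** A responder count is binomial, so the true error of any pair of count boundaries can be computed. At p = 0.2 the binomial is skewed to the right, and a normal approximation without continuity correction makes the upper tail look smaller than it is. A boundary that just meets the Z limit can then have a true tail above its allotted alpha. The final boundary takes over the interim's approximate spend rather than its true one, so it does not correct for this.

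The trial has one primary hypothesis, and 2.5% is its stated limit. The interim count was also the trigger for the Steering Committee to discuss an early regulatory filing, so the error at that look matters as well as the total.

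**Working it through.** **Inputs.** Null rate 0.2, alternative 0.35 and the planned 50/110 (Protocol 10.8 and 10.7); overall one-sided alpha 0.025 and the normal-approximation test (Protocol 10.4.2); Lan-DeMets spending, Table 10-2 and the recalculation rule (Protocol 10.7); 120 patients (SAP section 1).

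**Step 1: reproduce Table 10-2.**
- Spend at t = 50/110: 2[1 − Φ(z₀.₉₈₇₅/√t)] = 0.000886, so Z₁ = 3.126.
- Final Z from the bivariate normal with correlation √(50/110): Z₂ = 1.965.
- Required count: smallest r with (r − 0.2n)/√(0.16n) ≥ Z.
  - n = 50: r = 19 gives 9/2.828 = 3.18; r = 18 gives 2.83. Boundary 19.
  - n = 110: r = 31 gives 9/4.195 = 2.15; r = 30 gives 1.91. Boundary 31.
- Normal-approximation power at 0.35: 0.345 at the interim and 0.951 overall.

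All of this agrees with Table 10-2. A continuity correction would give 20/50, and an estimated variance would give 21/50 and 32/110. The plan therefore uses the null variance without correction.

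**Step 2: exact error at the planned size.** The two-stage error is P(X₅₀ ≥ r₁ or X_N ≥ r_N | p = 0.2). Interim crossings count, because alpha is spent on them and Table 10-2 labels the boundary as one that rejects the null hypothesis.

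| Rule | Exact probability at p = 0.2 |
|---|---|
| 19/50 alone | 0.00251 (2.8 times the spend of 0.000886) |
| 20/50 alone | 0.00093 |
| 30/110 alone | 0.0406 |
| 31/110 alone | 0.0247 |
| 19/50 then 31/110 | 0.02568 |
| 20/50 then 31/110 | 0.02497 |

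A simulation of 4 million trials of 19/50 then 31/110 gives 0.02566.

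**Step 3: the recalculation rule at other final sizes.** Interim 19/50, 0.000886 kept as spent, and Z₂ recomputed with correlation √(50/N), which gives about 1.966.

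| Final N | Count | Exact two-stage error | Final look alone |
|---|---|---|---|
| 111 | 31 | 2.88% | 2.79% |
| 112 | 31 | 3.22% | 3.14% |
| 113 | 31 | 3.60% | 3.52% |
| 114 | 32 | 2.51% | 2.41% |
| 115 | 32 | 2.81% | 2.71% |
| 116 | 32 | 3.14% | 3.05% |
| 117 | 32 | 3.50% | 3.41% |
| 118 | 33 | 2.45% | 2.35% |
| 119 | 33 | 2.74% | 2.64% |
| 120 | 33 | 3.06% | 2.96% |

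Nine of the ten sizes exceed 2.5%, and at eight the final look alone does. At 122 the rule gives 34 and 2.40%. Raising only the interim to 20/50 would leave 33/120 at 2.98%.

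**Step 4: smaller interim denominators.** If 1 to 4 of the first 50 had no baseline volume, the rule still requires 19.

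| Interim N | Spend | Exact tail of 19 | Ratio |
|---|---|---|---|
| 46 | 0.000528 | 0.00078 | 1.5 |
| 47 | 0.000606 | 0.00107 | 1.8 |
| 48 | 0.000691 | 0.00144 | 2.1 |
| 49 | 0.000784 | 0.00191 | 2.4 |

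**The case against.** The normal approximation is declared openly, so the 2.5% can be read as the nominal level of that test; on that reading the issue is a choice of method, not a miscalculation. It is true that Table 10-2 contains no error of computation. But Protocol 10.7 states an upper limit on the cumulative error, and declaring the approximation does not make that limit true.

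The planned design is barely affected. The excess at 110 is 0.07 percentage points, 31/110 alone is within the limit, and the interim cannot stop the trial. This stands: only a result of exactly 19/50 would be judged differently, and its probability is 10.5% if the true rate is 0.35.

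The count of nine in ten is sensitive. It becomes eight if the rounded p ≤ 0.024 limit is applied, if the exact interim error is taken as spent, if only the final look is counted, or if the interim size is 48, 49, 51, 52 or 53. The error moves in a sawtooth with N. This stands too, but most sizes exceed the limit under every variant, and at 120 the error stays at about 3.0% to 3.1%.

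The figure for 120 is conditional, and at that size the correction is one responder (33 to 34); exactly 33/120 has probability 1.7% at a true rate of 0.35. The Week 24 analysis plan may contain other boundaries. These points limit what can be said about the trial's result; they do not rescue the rule as written.

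**Conclusion.** The concern holds. The plan states a limit on type I error that its boundaries do not guarantee. At the planned 50/110 the exact error is 2.57%, a small excess that comes wholly from the interim. At most other sizes near the plan the excess is larger and usually affects the final look as well, reaching 3.60% at 113.

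The 3.06% at 120 assumes an interim of exactly 50, all 120 patients in the final denominator and the protocol's rule applied unchanged. Neither document prints 33/120, and N may not be 120 because patients without a baseline spleen volume are dropped. The finding concerns the rule, not the trial's conclusion.

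**What to change.** Replace the normal-approximation test with the exact binomial test, and set count boundaries at the actual N so that the exact two-stage error is at most 2.5%. At 50/110 this means 20/50 then 31/110. State the boundaries as counts, with matching exact p-value limits: 0.00093 for 20/50 and 0.0247 for 31/110. The interim tail of 20/50 is marginally above the 0.00089 spend, but the overall 2.5% is held.

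Made before the interim, the change would have cost only wording and re-derived counts, plus some power. At 50/110, exact final power is 0.9473 against 0.9477, and exact interim power falls from 0.378 to 0.274. At final sizes 111 to 120 with 20/50 at the interim, the exact rule has power 0.930 to 0.958, against 0.953 to 0.969 under the present rule.

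Since the interim and Week 24 analyses are already reported, the remaining step is to report the exact interim and final p-values, the boundary used at the actual N and its exact type I error. If RAP Module 3 Amendment 2 already gives these, a citation is enough.
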